(12) Pregnancy Intake Survey and Monthly Maternal Health/Medication Questionnaire: Upon enrollment, and then at each monthly obstetrical visit, the mother will be asked to complete a health assessment questionnaire to ascertain her use of medications (checklist) and over-the-counter preparations that may influence vitamin D/calcium homeostasis. She will be specifically asked questions regarding her use of cigarettes and alcohol, and overall health status. In addition, if mother has required hospitalization, this will be recorded and a copy of the hospital record obtained after she has signed a release of medical information form to obtain the medical information. In addition, e.g., if mother required tocolysis, antibiotics or IV rehydration, this will be recorded on the questionnaire.

(13) Maternal Dietary History: Each mother will complete a standardized Food Frequency Questionnaire (FFQ) at the 2nd visit to ascertain her generalized eating pattern, with specific calculation of calcium and vitamin D intake. A Diet and Lifestyle Questionnaire will also be distributed. [name] will use data obtained from the FFQ and Diet and Lifestyle Questionnaire to determine fish/shellfish consumption as it pertains to methylmercury intake and the interaction between vitamin D and methylmercury. This questionnaire is advantageous to collecting data over food diaries or 3-day food records for the following reasons: (a) The questionnaire does not rely on memory as much as other validated methods; (b) Its readability is designed for lower literacy populations; and (c) It accurately estimates individual and population-wide average daily intakes of all macro- and micronutrients. Individual and collective data can be gathered for statistical analysis to assess dietary intakes for this study population. This tool has been validated and reproduced against other dietary intake tools. Each completed FFQ form will be sent to the processing center (Berkeley, California) in batches of 50-100. Food models also will be provided to assist subjects in identifying most commonly consumed portion sizes rather than assuming each subject can accurately discern serving sizes on her own.

(14) Maternal Physical Activity Assessment Questionnaire: Each mother will be asked to complete a Physical Activity Assessment Questionnaire. This questionnaire utilizes a well-established physical activity instrument with known validity and reliability. Because physical activity can affect calcium metabolism and because a woman's activity level may change considerably during her pregnancy, it will be important to reassess maternal activity level throughout the entire period of gestation. Therefore, each mother will complete this questionnaire monthly.

(15) Sunlight Exposure: Two body sites will be scored at each monthly visit with a Smart Probe (measures skin color at 450 nm wavelength) to assess sunlight exposure.

(16) Maternal Physical Examination: As part of MUSC's OB clinic, each mother undergoes a physical examination at scheduled clinic visits, according to standard of care for the OB clinic. Some of these results of the physical exam will be recorded directly on the case report forms.

(17) Maternal Dental Examination: Women with 1 or more natural teeth and not having a health condition that requires antibiotic prophylaxis before periodontal probing are eligible for the periodontal examination.

(a) The commonly used full mouth periodontal examination (FMPE) may be done up to three times during the pregnancy (baseline, 28 weeks and 36 weeks). The FMPE protocol will be used for classification of periodontal disease. The major outcome measure of change in the periodontal measures will be correlated with change in serum circulating 25(OH)D concentration from baseline to 28 and 36 weeks. The FMPE will be done by trained personnel (Registered Dental Hygienist or Dentist) in a dental chair setting. Data are either recorded on paper or direct data entry will be done. The research instruments and questionnaires have all been previously used in the research environment.

(b) Gingival inflammation is measured using a salivary occult blood test (SOBT). The chairside SOBT is done monthly by rinsing the mouth with water and then spitting into a small paper cup. The outcome for SOBT will be analyzed with respect to the periodontal measures, and in particular, the percent of sites with BOP. Trained study personnel will perform the SOBT. Data will be recorded on visit questionnaire. This research instrument has been previously used in the research environment.

(c) Oral bacteria will be measured using a GenProbe for Chlamydia trachomatis at delivery or visit 7 (36 weeks). A swab is used to make the oral collection by gently swabbing the inside of the cheeks and oral cavity. The dichotomous outcome for Chlamydia (positive or negative) will be analyzed with respect to the periodontal measures, BOP, and birth outcomes. Trained study personnel will perform the oral bacterial test. Data will be recorded on the visit questionnaire. This research instrument has been previously used in the research environment.

(18) Labor and Delivery Questionnaire: Characteristics of each mother's labor and delivery will be recorded on a data form. Prior complications of pregnancy will be listed on the monthly pregnancy assessment questionnaire. Such complications at the time of delivery will be listed here according to ACOG definitions: e.g., preeclampsia; HELLP syndrome; gestational diabetes; hypertension; preterm labor; premature rupture of membranes (PROM); deep venous thrombosis or a coagulopathy; maternal infection such as varicella or herpes (primary or secondary); placental abnormalities such as previa or abruption. The following information about labor will be included: (a) length of labor, (b) use of pitocin augmentation, (c) time of rupture of membranes, and (d) complications of labor: fetal distress or decelerations, failure to progress, shoulder dystocia, breech presentation or abnormal fetal lie. Should the infant be delivered at an outlying hospital, mother will complete a release of medical information form so that medical records relating to the labor and delivery and the infant's health status/physical examination will be forwarded to the Clinical PI.

(19) Maternal Body Mass Index (BMI) Measurement: Pre-pregnancy height and weight of each mother will be recorded at the first outpatient visit to determine BMI (weight [kg]/height² [m²]). During subsequent outpatient visits, only the mother's weight will be recorded.

(20) Maternal Baseline and Monthly Calcium and C-Reactive Protein Serum Studies: Whole blood (3.5 mL) will be obtained from each mother at the time of her scheduled obstetrical visit monthly as well as at delivery and placed in an SST tube. The blood will be sent to the Clinical Chemistry Laboratory. The following blood studies will be measured: total Ca and C-reactive protein. These results will be reported directly to [name], then entered into the Study's Database.

(21) Maternal Baseline and Monthly Vitamin D and Calcium Homeostatic Parameters: A 14 mL sample of whole blood will be drawn from the mother at the scheduled obstetrical visit monthly as well as at delivery and placed in an SST tube to be processed in the CTRC Clinical Laboratory for serum separation. The serum will be placed in a -80°C freezer and sent to [name] laboratory on dry ice. Each serum sample will be analyzed for maternal circulating levels of total 25(OH)D, 1,25(OH)₂D, iPTH (5), batched for serum cytokine analysis, and batched for measurement of megalin and cubulin. 25(OH)D will be run on all subjects after 3 months supplementation. Mothers who are still frankly vitamin D deficient (less than 15 ng/ml) will be placed on open label vitamin D gummies for the remainder of their pregnancy.

(22) Monthly Maternal Urine Sample: A random urine sample will be obtained from the mother at each obstetrical visit to be sent to the Clinical Chemistry Laboratory for urinary Ca and creatinine measurement and derivation of the urinary Ca: creatinine ratio. This ratio will be used as an indicator of hypercalciuria that precedes hypercalcemia. Results of these urine studies will be reported directly to [name]. An additional aliquot of the urine sample will be frozen for future cytokine analysis.

(23) Cord Blood Vitamin D and Calcium Measurements. At the time of delivery, 10-mL of whole blood will be drawn from the umbilical vein then sent to the CTRC Clinical Laboratory facility for processing. One red bullet (0.5 cc aliquot) will be sent to the Clinical Chemistry laboratory for measurement of total calcium and creatinine. The remaining blood will be processed in the CTRC Clinical Laboratory immediately for serum separation and placed in a -80° C freezer then transported on dry ice to [name] laboratory for later determination of each neonate's circulating levels (at the time of delivery) of intact iPTH, total 25(OH)D, and 1,25(OH)₂D (5). Additional frozen serum will be batched for analysis of cytokines. Every effort will be made to collect cord blood at the time of delivery. An additional 15 mL plasma sample will be obtained from the cord for immune privilege flow cytometry studies.

(24) Immune Privilege Flow Cytometry Studies: Maternal plasma (14 mL) at first visit (baseline), fourth visit (24 weeks gestation) and seventh visit (36 weeks gestation), as well as 15 mL cord plasma will be analyzed by [name] laboratory for circulating immune cells by flow cytometric analysis. Plasma cytokines will be measured by ELISA per manufacturer's instructions. Expression of genes related to

vitamin D₃ activation and metabolism will be measured by custom PCR Array (SA Biosciences) for the following genes: VDR (vitamin D receptor), CYP2R1 (vitamin D 25-hydroxylase), CYP27B1 (1-alpha-hydroxylase), CYP24A1 (24-hydroxylase), and GC (vitamin D binding protein). The plasma immunoregulatory products to be examined include IL-10, TGF-beta, TNF-alpha, IFN-gamma, IL-2, IL-18 and IL-12.

(25) Vaginal Self-Swabs: At each visit, subjects will be asked to perform 3 vaginal self-swabs:

(a) First swab that the study coordinator will use to prepare a wet mount slide for identification of bacterial vaginosis and gram staining (these slides will be air dried and saved for batch analysis by the pathologists in Clinical Chemistry);

(b) Second swab will be a GenProbe swab for identification of Trichomonas vaginalis, Neisseria gonorrheae and Chlamydia trachomatis;

(c) Third swab will be a GenProbe swab for evaluation of vaginal cytokines. When study subjects come into hospital for delivery, we will also obtain these three vaginal self-swabs. Vaginal cytokines that are of interest include: tumor necrosis factor- α , interleukin (IL)-1- α and 1- β , IL-2, IL-3, IL-4, IL-5, IL-6, IL-7, IL-8, IL-10, IL-12, IL13, IL-15, IL-17, IL-18, monocyte chemotactic protein (MCP), TGF- β , macrophage inflammatory protein (MIP), alpha-defensins, leukotriene B, s-tumor necrosis factor-R1, E-selectin, necrosis factor and cAMP element response binding. These cytokines can be batch-analyzed using a custom Luminex multiplex ELISA assay.

(26) Placental Pathology Placentas will be obtained at time of delivery for research purposes. Each placenta will be placed in the Labor and Delivery refrigerator until transport to Pathology, [name] lab refrigerator. [name] will record gross placental findings, membranes, fetal surface, maternal surface, and placental parenchyma, using methodology already in place in [name] pathology laboratory.

(27) DNA and mRNA Expression: At visit 2, each study subject will have an additional 6 mL of blood drawn in a plasma tube for analysis of DNA and RNA by [name] lab. Specifically, vitamin D binding protein DNA and vitamin D receptor will be analyzed per subject as per established protocol. mRNA expression of CYP24A1, CYP27B1, IL-4, IFNg, IL-6, IL-17A, IL-23, FoxP3, and 24,25(OH)2D also will be measured using methodology already in place in [name] laboratory and previously reported (118).

(28) Methylation: Cord blood, buccal mucosal swabs, and placental tissue samples will be used to determine the variation in infant DNA methylation as a function of maternal vitamin D status, maternal pregnancy complications, and infant and maternal characteristics. The methylation will be probed at both the whole genome level and at the specific locus level. To evaluate the methylation status of the entire genome we will utilize a liquid chromatography-mass spectroscopy based method, which determines the proportion of methylated cytosine to total cytosine in the entire genome. We will use locus-specific methylation probes to determine the methylation of the promoter regions for cortisol receptor, vitamin D receptor, and other steroid receptor sites. Locus-specific methylation will be determined by bisulfite sequencing to determine the methylation of individual cytosine base pairs at the nucleotide level.

(29) Metabolism and Processing of Vitamin D: [name] will examine the effect of dietary methylmercury intake on the metabolism and processing of vitamin D supplementation during pregnancy. A recent publication reported the ability of methylmercury to inhibit the bioactive form of vitamin D to upregulate the vitamin D receptor, thereby potentially negatively altering the innate immune system (119). To examine this pathway in this cohort, at visits 2, 7 and delivery, each study subject will have an additional 6 mL (1.2 teaspoons) of whole blood drawn in a royal blue vacutainer. Additionally, data obtained from both the FFQ and Diet and Lifestyle Questionnaire will determine fish/shellfish consumption as it pertains to methylmercury intake. The methylmercury levels will be determined and compared with the vitamin D status and vitamin D receptor gene expression of the subjects.

(30) Child Dental Visit At 18 months of age, the dentist or hygienist will ask routine dental utilization questions, examine and make digital images (take photographs) of the child's teeth. Likewise, an oral bacterial collection may be done by a gentle swabbing of the mouth.

Activity #7 (Objective #3): Through the joint efforts of this Kellogg-sponsored project, the Medical University of South Carolina and GrassrootsHealth.net, activity #7 represents a significant public health breakthrough. GrassrootsHealth.net is a nonprofit organization located in San Diego and affiliated with the University of California in San Diego, whose sole purpose is to improve the health of individuals throughout the world through education about vitamin D and the adverse effects on health during times of deficiency. Through the assistance of GrassrootsHealth.net and the University of California's San Diego's CME office, we developed educational media and CME credits for physicians and other health care professionals to teach them about vitamin D, its role in immune function and overall health, with the latest scientific information (GrassrootsHealth.net received funding for this during year 4 of the Kellogg project).

We launched "Protect Our Children Now" campaign on April 7, 2015. Protect Our Children NOW! is a community outreach and clinical implementation project to reduce the incidence of preterm births quickly, easily, and safely by addressing the vitamin D deficiency epidemic through the engagement of pregnant women in a valuechanging program of Good Health vs. 'Treating Illness.' The purpose is to implement vitamin D testing and supplementation of pregnant women as standard of care. Specifically, it is to help them achieve a serum level of at least 40 ng/mL to aid in the prevention of many comorbidities of pregnancy.

The Protect Our Children NOW! project involves educating prenatal care practitioners by providing free CME opportunities about vitamin D, and the importance of testing serum levels. These CME courses were and are offered to MUSC physicians sponsored by the University of California San Diego and GrassrootsHealth. In addition to the CME credits, each physician and health care provider receives 'D*certification' for this project.

Once again, these goals can only be reached when the Obstetrical community embraces the importance of vitamin D supplementation during pregnancy as an important factor in affecting the outcome of the health and well-being of the mother and the developing fetus during pregnancy. To this end, MUSC has partnered with GrassrootsHealth to implement universal vitamin D screening of all pregnant women who present to MUSC for their obstetrical care.

The Obstetrics Department at MUSC embraced the mounting evidence that vitamin D deficiency is not beneficial to our pregnant women and began universal screening in September 2015 of all pregnant women presenting for obstetrical care at MUSC. Specifically, all pregnant women who present for obstetrical care within the MUSC system have a baseline 25(OH)D concentration measured with appropriate counseling and supplementation to achieve a total circulating 25(OH)D concentration of at least 40 ng/mL by second trimester with repeat measure now enacted at the 24-28 weeks' gestation obstetrical visit to coincide with the planned glucose tolerance test. This change in practice began on September 1, 2015, after the Obstetrics Department at MUSC unanimously agreed to implement this change. Without surveillance data, however, there is no way to assess the effectiveness of this program and its impact on pregnancy outcomes at MUSC. To address this deficit, we have implemented the following:

Methods for Activity #7 (Objective #3):

Using the MUSC Perinatal Database and the associated laboratory data, the vitamin D status of all women who present for obstetrical care at MUSC and who deliver their infants at MUSC will be assessed. We will request a waiver of consent and HIPAA as it is not practical to consent these women and their babies after they have been discharged, and the data will be queried in a manner that will reduce the risk of loss of confidentiality by utilizing deidentified data after the laboratory data are merged with the PINS database by [name]. The data to be abstracted from PINS includes complications of the pregnancy, complications of the delivery and abnormal diagnoses of the offspring child. The data will be used to address specific research questions as noted above. Grassroots Health will analyze the deidentified data as an independent entity that is already involved in the Kellogg Vitamin D Pregnancy Project.

E. PROTECTION OF HUMAN SUBJECTS

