Study Design: This is a randomized, placebo-controlled clinical trial of 450 pregnant women who will be enrolled between 10-14 weeks of gestation and followed until delivery. Following written, informed consent, each mother will be randomized to receive either placebo or 4000 IU/day vitamin D₃ plus the standard prenatal vitamin (containing 400 IU vitamin D₃). She will be followed monthly for a total of nine study visits. If, after 3 months of vitamin D supplementation, a mother is still frankly vitamin D deficient (less than 15 ng/ml), she will receive open label active vitamin D gummies for the remainder of her pregnancy. These visits will include the initial recruitment of mother at 10-14 weeks of pregnancy, monthly study visits, delivery study visit, and 18-month post-partum follow-up visit for mother and child. The primary outcome variable is maternal and neonatal health status as a function of maternal and infant vitamin D status. Secondary outcome variables to be analyzed, as a function of maternal vitamin D status during pregnancy will include: T-lymphocyte profile, immune function indicators, neonatal growth, inflammatory cytokine profile, methylation patterns of DNA of both mother and her neonate,

(1) Subject Selection Criteria and Recruitment: Any mother (18-45 years of age) who presents to her obstetrician or midwife at the Medical University of SC (MUSC), Charleston, SC obstetrical facilities within the first 14 weeks after her last menstrual period (LMP) with confirmation of a singleton pregnancy will be eligible for enrollment in the study. Mothers of diverse ethnic backgrounds (African-American, Asian, Caucasian and Hispanic) will be actively recruited. A database will be generated weekly of undelivered patients for the labor and delivery staff continue to alert the staff of impending admissions.

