Preventing Health Disparities during Pregnancy through Vitamin D Supplementation

NCT#01932788

11/6/2013

Statistical Analysis: The primary analysis in this investigation will compare levels of maternal 25(OH)D across the two supplementation groups as 'Intention-to-Treat' and will employ Mantel-Haenszel mean scores; however, a 'Per Protocol' (oversampling to consider attrition) analysis also will be done. This two-step analysis provides information regarding the efficacy of these dosage levels in increasing vitamin D and the effectiveness of oral supplementation to increase vitamin D. Whether the losses are random or are biased with respect to ethnicity, or supplementation arm will be tested. Any differential losses will be reported and examined with the use of propensity scores.

Because of the unique nature of the contributions of potential confounders, two approaches to the analysis will be employed. The first and primary analysis will use a Mantel-Haenszel estimate of the mean treatment difference, computed from stratum-specific treatment differences, which will utilize a weighted average of treatment differences across ethnicity. Mean differences will be calculated for the experimental dosage relative to the 400 IU group. Bonferroni adjustments will be made for the Type I per comparison error rates to correct for multiple testing. The treatment differences, estimated variances, and confidence intervals for the differences will be estimated for maternal serum 25(OH)D. This mode of analysis is quite effective in clinical trials as it is less dependent on normal theory assumptions and associated assumptions such as homogeneity of variance. Parametric models also will be fit, but the primary analysis will rest on Mantel-Haenszel mean scores techniques readily done within SAS. Parametric dose response curves also will be generated to describe the relationship between 25 (OH)D and dosage.

The proportion of participants who completed the daily supplement regimen will be estimated, with a similar "per protocol" style analysis restricted to those individuals. Finally, techniques of multiple linear regression will be employed to describe the interactive effects of ethnicity, as well as the effects of other covariates, such as seasonality, mother's age and fecundity, on baseline serum 25(OH)D. These models will be assessed for violations of the model assumptions, and corrected for such violations as appropriate.

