The second statistical approach measures the effects of the confounders and takes the more traditional approach of assuming normal distribution for Vitamin D, and will be performed in parallel fashion to compare treatment effects in 400 IU and 4400 IU vitamin D groups. The primary research aim is to determine if supplementation is associated with an increase in vitamin D concentrations. As discussed below, it will be necessary to identify and control for other factors (confounders) that may also be associated with changes in vitamin D levels.

Paired analyses according to the study plan will be conducted by employing McNemar chisquare for categorical variables, paired t-tests for normally distributed variables, repeated measures ANOVA for longitudinal analyses, and multiple linear regression for multi-variable analyses to control for confounding. Correlation will be used to assess the linear association between outcomes and those factors expected of an accumulated dose-response relationship (e.g., sunlight exposure), and individual regression tests to identify the strength of the association between outcomes and each characteristic. The resulting coefficients then will be translated into a formula for the linear association between each factor and outcomes. In the event that there are non-linear distributions, appropriate data transformations will occur as necessary.

Both groups will be compared for differences in any factors at baseline, and will include: information contained in the maternal sociodemographic, maternal pregnancy and delivery, and maternal calcium, creatinine, vitamin D₃, 25(OH)D, and urinary calcium creatinine ratio. While the stratified blocked randomization technique should minimize the potential for baseline differences, this first step will confirm whether there should be adjustment for any initial differences in follow-up analyses. Next, differences between baseline and follow-up will be examined for those variables that may have changed over the follow-up period (health assessment; physical activity; and blood and urine outcome measures) to identify those factors that may serve as confounders or effect modifiers for the vitamin D assessments. The potential influence of identified confounders or interaction terms will have to be considered for any change in vitamin D status.

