Changes in vitamin D outcomes will be compared between treatment arms with the additional information from sunlight exposure, pigmentation/melanin index, maternal physical activity assessment, maternal dietary history, health, and medication questionnaires. This detail will allow the separation of changes in vitamin D parameters as a function of confounding factors from supplementation. The study is powered to explore the degree to which changes in vitamin D parameters are a function of supplementation and ethnicity. To assess whether there are differences in the slopes or linear dissimilarities in the outcomes over time, repeated measures techniques will be used to compare longitudinal changes in outcomes between groups. This technique also provides a graphical depiction of the slopes over time and can identify if there are linear or plateau responses to differences in vitamin D supplementation concentration; it also will allow determination of data transformation techniques required for subsequent analyses if the slopes over time are non-linear.

The final step in the second statistical approach will determine whether potential group differences in the various outcomes are a function of any of the potential confounders—with particular attention to skin pigmentation and sunlight exposure. This step will identify changes in outcomes associated with population factors independent of the group (supplementation) assignment. The extent of more complex statistical analyses will be predicated on the number of individuals comprising specific strata, and thus, restricted by a reduction in the statistical power. Such comparisons will be reported as information for future studies. To clarify, using sunlight exposure as a representative example, the independent effect of vitamin D supplementation may be found to have been modified by the amount of sunlight exposure. As such, the changes in outcomes attributable to each factor, independently, and then when considered in combination will be partitioned. While the major goal of this study is to examine the various outcomes as an independent function of vitamin D supplementation—thereby controlling for all other group differences, the changes in outcomes that are associated with these group differences will be examined and reported in detail. In this way, the changes in vitamin D that are associated with each factor independently will be partitioned.

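### The protocol and SAP name different primaries (health status by achieved vitamin D level; maternal 25(OH)D by arm), and no named health outcome has a specified between-arm test

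*Protocol*

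**What the plan says.** **Protocol (6/17/2016).** Section D, Study Design: "The primary outcome variable is maternal and neonatal health status as a function of maternal and infant vitamin D status". The secondaries follow the same pattern: "Secondary outcome variables to be analyzed, as a function of maternal vitamin D status during pregnancy will include" the T-lymphocyte profile, immune indicators, neonatal growth and others. Section D(17) correlates periodontal change with change in 25(OH)D, and relates the oral Chlamydia result to periodontal measures and birth outcomes.

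**SAP (11/6/2013).** The opening sentence says: "The primary analysis in this investigation will compare levels of maternal 25(OH)D across the two supplementation groups", by intention-to-treat, with a Mantel-Haenszel mean difference across ethnicity. The second approach gives the matching aim: "The primary research aim is to determine if supplementation is associated with an increase in vitamin D concentrations". Power is tied to vitamin D parameters.

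A general by-arm intent is present. The protocol's Specific Aims compare 400 with 4000 IU/day. The SAP's last paragraph says "the major goal of this study is to examine the various outcomes as an independent function of vitamin D supplementation", without listing those outcomes.

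**The concern.** In the protocol vitamin D status is the explanatory variable; in the SAP it is the outcome. A trial report could present either as the prespecified primary.

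If the protocol wording is followed, the primary clinical contrast is observational. Women who reach a higher 25(OH)D may differ in diet, sun exposure, adherence and general health. The documents accept this. The SAP says "it will be necessary to identify and control for other factors (confounders) that may also be associated with changes in vitamin D levels". Protocol section C leaves open whether level is only a marker of something else. Section E.4 says the earlier trials' post-hoc analyses, which include those by 25(OH)D level, can suggest no more than correlation. Yet the same section hopes that this randomised trial will show differences in comorbidities.

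**Working it through.** **1. The two primaries side by side**

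| | Protocol, Study Design | SAP |
|---|---|---|
| Outcome | Maternal and neonatal health status | Maternal 25(OH)D |
| Contrast | Achieved vitamin D status, mother and infant | Randomised arm |
| Components or time point | None given | None given |
| Test | None given | Mantel-Haenszel mean difference, stratified by ethnicity |

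**2. Search for a between-arm test of a named health outcome**

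- SAP, first approach: treatment differences and confidence intervals are stated for maternal serum 25(OH)D only.
- SAP, second approach, categorical data: "Paired analyses according to the study plan will be conducted by employing McNemar chisquare for categorical variables". McNemar's test is for paired data, so it does not compare independent arms.
- SAP, second approach, group comparison at baseline: covers "information contained in the maternal sociodemographic, maternal pregnancy and delivery". The health assessment is screened as a possible confounder or effect modifier.
- SAP, repeated measures between groups: the outcomes are unnamed, and a once-per-pregnancy event such as preeclampsia is not a slope over time.
- Protocol D(17) and D(18): complications are recorded by ACOG definitions, but no by-arm test is given.

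None is found.

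**3. Does the choice of contrast matter?** Section C's combined cohort found no difference between groups in single or combined comorbidities. By level, the odds ratio was 0.84 per 10 ng/mL (95% CI 0.74-0.96, p=0.0095). Section C also reports a by-dose result the other way: fewer combined events at 4000 IU across three doses, p=0.03.

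**4. The plan's own sample size.** Section E.1 requires 300 completers for power but gives no effect size, SD, event rate, alpha or power, so 300 cannot be reproduced. (Enrolment of 450 is more than 300/0.70 = 429 and leaves 450 × 0.70 = 315 completers. That is conservative and not at issue here.) Section D(8) takes all outcome markers as normally distributed, although D(17) names a dichotomous one.

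**5. Size of the consequence (illustration).** Inputs: 150 completers per arm (E.1, half of 300) and the odds ratio and CI above. Assumed, because the documents do not give them: two-sided alpha 0.05, control risk 20% or 40%, and a gap in mean 25(OH)D between arms of 10, 15 or 20 ng/mL. The odds ratio is also taken as fully causal.

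- Between-arm OR = (OR per 10 ng/mL)^(gap/10); treated risk = odds/(1 + odds).
- Power = Φ[(|p₁−p₂| − 1.96·√(2p̄(1−p̄)/n)) / √((p₁(1−p₁)+p₂(1−p₂))/n)].
- Example, OR 0.84, gap 20, control risk 0.40: OR = 0.84² = 0.706; odds = 0.667 × 0.706 = 0.470; treated risk = 0.320; power = Φ[(0.0801 − 1.96 × 0.0554)/0.0552] = Φ(−0.52) = 0.30.

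| OR per 10 ng/mL | Control risk | Power at gap 10 / 15 / 20 | n per arm for 80% power, gap 10 to gap 20 |
|---|---|---|---|
| 0.84 | 40% | 11 / 19 / 30% | 2,196 to 563 |
| 0.84 | 20% | 9 / 14 / 21% | 3,408 to 904 |
| 0.74 | 40% | 24 / 46 / 68% | up to the gap-20 value of 198 |
| 0.74 | 20% | 17 / 31 / 47% | up to the gap-20 value of 333 |
| 0.96 | 40% | 3.7 / 4.4 / 5.3% | from the gap-10 value of 39,416 |
| 0.96 | 20% | 3.4 / 4.0 / 4.6% | from the gap-10 value of 59,608 |

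Power counts rejection in the expected direction only, which is why some entries fall below 5%.

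Detectable at 80% power with 150 per arm: 40% vs 24.9%, 30% vs 16.4%, 20% vs 8.7%.

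25(OH)D by arm: the standard error is SD × √(2/150). At SD 13 this is 1.50, so the detectable difference is 2.80 × 1.50 = 4.2 ng/mL (3.2 at SD 10, 5.2 at SD 16). Power for 10 ng/mL at SD 16 is Φ(10/1.848 − 1.96) = 0.9997, and it is higher at SD 10 and 13. The SD of about 13 comes from section C's trial of 2000 against 4000 IU, which had no 400 IU arm.

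**The case against.** **The SAP already protects the primary.** It is the only document with an analysis plan, and its primary is by arm, intention-to-treat and ethnicity-stratified, with power tied to the same variable. The non-randomised primary arises only if the protocol is followed. That is true, but the protocol carries the later date and neither document gives way to the other.

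**The SAP does have by-arm language beyond 25(OH)D.** It promises repeated measures between groups and a final step on group differences in various outcomes. This stands as general intent. It names no complication, time point or unpaired test for a yes/no outcome. The baseline sentence is weak evidence either way, since delivery data cannot exist at baseline.

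**The sizing rests on assumptions.** The ranges are wide, and taking the odds ratio as causal is the very inference called unsafe above. That is fair: the figures show only that the two primaries are not interchangeable, and the textual finding does not need them. The missing power inputs affect every endpoint, not only yes/no ones.

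**The earlier null by arm should not be over-read.** On the same assumptions, 110 women on 400 IU against 189 on 4000 IU gives 9-29% power at OR 0.84 (3-66% over the CI). That leaves out the 197 women on 2000 IU. A three-group test with the middle dose midway gives about 8-23%. Either way the null does not settle the question.

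**New by-arm tests need a place in the Bonferroni plan, and interim efficacy looks are foreseen (section E.5.C).** Both points stand and are taken into the fix.

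**Conclusion.** The concern holds, with high confidence, and must be fixed. The two documents name primaries that differ in outcome and in contrast, with nothing to reconcile them. Followed as written, the protocol gives a non-randomised primary in a randomised trial. No named health outcome has a specified between-arm test. This conclusion rests on the text alone.

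The size is illustrative. The planned completers are ample for 25(OH)D by arm (over 99.9% power for 10 ng/mL at SD 10-16). They give about 9-30% power for a complication at OR 0.84, and about 3-68% over its confidence interval, under the assumed control risks and arm gaps. The required statistical power asserted in section E.1 is therefore not shown for a yes/no health outcome.

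**What to change.** 1. **State one primary, by randomised arm and with a time point, in both documents.** 25(OH)D is drawn monthly and at delivery (D(21)); the earlier combined analysis used values within one month of delivery. 25(OH)D by arm matches the SAP's stated analysis and power. If it is chosen, the amendment should say that it replaces the protocol's health-status primary. If health status stays primary, define it by arm and power it on an event rate supplied by the sponsor.
2. **Specify the complications analysis.**
   - Analyse the comorbidities listed in section C by arm, intention-to-treat, in the main ethnicity-stratified cohort. Women who move to open-label supplement stay in their randomised arm for analysis.
   - Use an ethnicity-stratified Mantel-Haenszel risk difference with 95% CI, and state its place in the Bonferroni plan.
   - Name the maternal and neonatal components; apart from preterm birth, the section C list is maternal. The sponsor should define the rule for any composite.
   - Separate bacterial vaginosis found at the first-visit swab from new cases.
   - Report the separately randomised known-disease subgroup (E.1) on its own.
3. **Label every analysis by vitamin D status exploratory and observational.**
4. **Limit D(8)'s distribution statement to continuous markers, and E.1's power statement to the vitamin D comparison,** unless an event rate is supplied. Any detectable difference for complications should be shown over a range of control risks marked as assumed (for example 40% vs 25%, 20% vs 8.7%).

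**Cost.** A protocol and SAP amendment, dated before arm-level outcome data are seen and stating who has had access through interim reports. No new women or data are needed, since arm, complications and swabs are already recorded. The downside is that health status by level loses primary status. If 25(OH)D is chosen, the primary is a biomarker result that earlier data already make likely (p<0.0001 between groups near delivery), while section C says that trials powered for health outcomes are still needed.
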